
Objectives

The purpose of this study is to assess the efficacy of intraoperative intravenous nonsteroidal antiinflammatory drug (ketorolac) versus intravenous (dexamethasone) administration on dysphagia and dysphonia after ACDF. Primary measures for dysphagia include the classification of the Bazaz and EAT-10 outcome results. The primary measures for Dysphonia will be analyzed by the Voice Handicap Index (VHI-10). Secondary measurements include result classification utilizing results from the Neck Disability Index(NDI) and Visual Analogue Pain Scale (VAS) for neck pain. Additional measurements to be analyzed are comparisons in complication factors in surgical site infection, need for re-operation and pseudoarthrosis.

Design

An on-line randomization generator will be used www.researchrandomizer.org.

Randomization will be an equal split between the three groups with no predictable pattern. The subject has a one in three chance of being randomized to any of the three different groups.

Subjects are blinded to the randomization assignment. This is a single blinded study. The treating physician and study personnel will know which group the subject is randomized into.

The lead study coordinator will track the randomization assignments, withdrawals and study completions. Once 25 from each of the 3 groups have completed the study, the study will cease enrollment.

Methods

Each study participant will have equal chance of being assigned to one of the three study groups. The subjects medical record will be reviewed and the data collected/documented will include: gender, age, diagnosis or reason for surgery, co-morbidities, medications, BMI pre-operative and post-operatively. All clinic follow-up progress notes will be reviewed to specifically collect any findings documented as complications from surgery.

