Subjects who elect to consent into the study will be assigned a random study number and randomized into three cohorts: control (no steroid or NSAID), IV NSAID (1-time dose of 30 mg of IV ketorolac at the time of closure), and IV steroid (1-time dose of 10 mg of IV dexamethasone at the time of closure). Randomization schedule will be performed in a 1:1:1 fashion. Patients will be blinded with regard to which treatment they received until at least 1 year after surgery. Those subjects whom willingly volunteer to be part of the study will be notified promptly if they are found to not meet trial criteria and advised that they will be automatically withdrawn from the study.

Patient outcomes (patient completed questionnaires to evaluate for dysphagia and dysphonia) will be collected preoperatively and at 1 day (post-surgical day to day 3 post-op), 3 weeks (+/- one week), 6 weeks (+/- two weeks), 3 months (+/- three weeks), 6 months (+/- one month), and 1 year (+/- three months) postoperatively and will include: The Eating Assessment Tool (EAT-10), The Voice Handicap Index (VHI-10), Neck Disability Index (NDI), and Visual Analogue Pain Scale (VAS), Bazaz classification for dysphagia.

Post operative questionnaire collection will occur at time of outpatient clinic follow-up or subject may be called by phone and data collected over the phone or questionnaires mailed if patient preference. (Clinic visit follow up per the usual standard of medical care is per the above data collection timeline points, however, many times patients are feeling better and do not return for all suggested follow-up).

Eligibility

Inclusion

>/= 19 years of age Undergoing ACDF for radiculopathy or myelopathy No known allergies or sensitivities to steroid or non-steroidal medications This is not an ACDF revision procedure or surgery related to treatment of trauma, infection or tumor.

Exclusion

Procedure is being done for revision, trauma, infection or tumor. Patients with known diagnosed metabolic diseases (diabetes, pancreatitis, gout, electrolyte imbalances, hypertension, hematological abnormalities including gastrointestinal bleeding...) Patients with known kidney disease or a creatinine level above the upper limit of normal > 1.27) (BMet labs are completed pre-operatively as standard of care on all patients unless there is documentation of normal labs completed within the past 6 months of surgery).

Patients with known allergy or sensitivities to steroid or non-steroidal medications

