
Statistical Analysis Plan

For dysphagia, primary outcome measures will be the Bazaz classification and the EAT-10. For dysphonia, primary outcomes will be measured by the VHI-10. Secondary outcomes will be measured with Neck Disability Index (NDI), Visual Analogue Pain Scale (VAS) for neck pain. Complications will also be documented for comparison to include: surgical site infection, need for reoperation and pseudoarthrosis.

Descriptive statistics (specifically counts and percentages) will be computed for all variables to ensure data quality and to evaluate the assumptions of statistical tests. Fisher's exact test will be used to evaluate associations between treatment groups and categorical measures at each time point. Analysis of variance (ANOVA) or the Kruskal-Wallis test, depending on the distribution of the data, will be utilized to compare continuous variables between the groups. If the overall p-value from ANOVA is statistically significant, pairwise comparisons will be performed and adjusted using Tukey's method. Mixed effect models also will be explored, with time, treatment group, and time x treatment group interaction terms as fixed effects and with a random intercept term to account for repeated measures All tests will be 2-sided and a p-value < 0.05 will be considered statistically significant.

No analysis was ultimately completed due to poor follow-up and lack of data.

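### The SAP specifies no between-group estimate or confidence interval and gates pairwise comparison on a significant ANOVA, so the ketorolac-dexamethasone question can end in one three-group p-value

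*Combined protocol and SAP*

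**What the plan says.** The Objectives section sets the question: "The purpose of this study is to assess the efficacy of intraoperative intravenous nonsteroidal antiinflammatory drug (ketorolac) versus intravenous (dexamethasone) administration". The Design section fixes the size: "Once 25 from each of the 3 groups have completed the study, the study will cease enrollment". Allocation is 1:1:1 to control, ketorolac and dexamethasone.

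The Statistical Analysis Plan section contains these elements:

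- **Summaries.** "Descriptive statistics (specifically counts and percentages) will be computed for all variables"; the purpose given is to check data quality and test assumptions. Reporting by arm is not mentioned, and no mean, SD, median or quartile is named.
- **Categorical outcomes.** "Fisher's exact test will be used to evaluate associations between treatment groups and categorical measures at each time point". No pairwise step follows.
- **Continuous outcomes.** "Analysis of variance (ANOVA) or the Kruskal-Wallis test, depending on the distribution of the data, will be utilized to compare continuous variables between the groups". Tukey-adjusted pairwise comparisons follow only if the overall ANOVA is significant. No pairwise step is given after Kruskal-Wallis.
- **Mixed models.** These are to be explored, with time, group and their interaction as fixed effects. No contrast, visit or interval is specified for reporting.
- **Decision rule.** "All tests will be 2-sided and a p-value < 0.05 will be considered statistically significant".

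The section ends by stating that no analysis was completed, because follow-up was poor and data were lacking.

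**The concern.** The question is a contrast between two drugs, but every test to which the plan commits compares three groups at once. A three-group p-value does not say which arms differ, in which direction or by how much. The two-drug contrast appears on one route only: a continuous outcome, analysed by ANOVA, with a significant overall result. On the other routes it does not appear, even when the overall test is significant. Bazaz, a primary outcome that the protocol treats as a classification, would go to Fisher's test and so has no planned two-drug comparison.

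The descriptive sentence does not fill the gap. Counts and percentages are natural for Bazaz and complications, but they do not give the centre or spread of a numeric score.

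At stake is how a non-significant result would be read. Without an estimate and interval, a reader cannot separate evidence that the drugs perform alike from a trial too small to tell. The plan has no equivalence or non-inferiority margin that would support a claim of similar efficacy.

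**Working it through.** The plan derives no sample size and states no effect size, SD or arm rates, so there is no power figure to reproduce. The check asks what 25 per arm can resolve.

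**Inputs from the documents.** n = 25 per arm (Design); three arms, 1:1:1 (Design, Methods); two-sided 0.05 (Statistical Analysis Plan). **Assumed by this review:** normal scores with a common SD, all effects in SD units, and the illustrative counts in steps 3 and 4.

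**1. Pairwise mean difference, unadjusted.** Half-width = t(0.975, 48) × √(2/25) = 2.011 × 0.2828 = 0.569 SD.

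**2. Pairwise mean difference, Tukey, three groups.** The studentized range quantile q(0.95; 3, 72) is 3.384. Half-width = (3.384/√2) × 0.2828 = 0.677 SD.

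**3. Binary outcome, 10/25 in both arms.** The Wilson limits for 0.40 are 0.234 and 0.593. Newcombe half-width = √[(0.400 − 0.234)² + (0.593 − 0.400)²] = 0.254. Identical observed rates are thus compatible with a difference of about 25 points either way.

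**4. Binary outcome, 12/25 against 8/25.** Fisher's two-sided p = 0.39. The risk difference is 0.48 − 0.32 = 0.16. The Wald half-width is 1.96 × √(0.48 × 0.52/25 + 0.32 × 0.68/25) = 0.268, so the interval runs from about −11 to +43 points. The p-value alone hides that a large difference is not excluded.

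**5. How often the ANOVA gate stays shut.** Assume a true difference of 0.5 SD between the drugs. The F test has 2 and 72 degrees of freedom, critical value 3.124 and noncentrality λ = 25 × Σ(μᵢ − μ̄)². Each row keeps the 0.5 SD drug difference and moves control.

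| Benefit over control of the two drugs (SD) | λ | Power | Not significant |
|---|---|---|---|
| −0.25 and +0.25 (control midway) | 3.125 | 32% | 68% |
| 0 and 0.5 (control equals one drug) | 4.167 | 42% | 58% |
| 0.25 and 0.75 | 7.292 | 65% | 35% |
| 0.3 and 0.8 | 8.167 | 71% | 29% |
| 0.5 and 1.0 | 12.5 | 88% | 12% |

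In the last column's share of trials, the ANOVA route ends with one overall p-value and no planned estimate of the drug difference. These are figures per test, for one outcome at one visit.

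**The case against.** Five points can be made for the plan.

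- **Non-significance need not be the likely result.** A reader might infer that p ≥ 0.05 is the most probable outcome at this size. The documents give no effect size, SD or arm rates, so they do not support that. A pairwise t test at 25 per arm has 50% power at about 0.57 SD and about 79% at 0.8 SD. The 68% figure needs control midway between the drugs, which makes one drug worse than no treatment. That fits poorly with the Background, which reports that steroids reduced dysphagia. These statements are also per test, whereas three primary outcomes at six postoperative visits give 18. This objection stands, so a range is given.
- **The plan would not be silent on efficacy.** A reader might infer that the output would say nothing about it. That goes too far. If counts were shown by arm, a risk difference could be derived for Bazaz and complications. The Background gives cut-offs for EAT-10 and VHI-10, so counts could also describe categorised scores. The mixed model would yield between-arm differences without the ANOVA gate. But reporting by arm is not stated, no categorised analysis of the scores is specified, and the mixed model is exploratory with no named contrast or interval.
- **The descriptive sentence does not forbid other summaries.** Its stated purpose is data quality and checking assumptions. That is fair: it is incomplete rather than prohibitive. But no other sentence in the plan supplies the missing summaries.
- **Nothing was misreported.** No analysis was completed, and no passage plans to claim equal efficacy. This limits the point to the plan itself and to any reuse of the plan or the collected data.
- **Reporting every contrast creates multiplicity.** Three pairs for five questionnaires at six postoperative visits make 3 × 5 × 6 = 90 intervals. This is a real cost and shapes the fix.

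**Conclusion.** The point holds as a defect of the plan. No between-group estimate or interval is specified, the numeric scores have no suitable summary, and the two-drug contrast is open only after a significant ANOVA. Followed as written, the committed analyses can leave the trial's own question without an estimate.

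The 95% half-widths, about 0.57 SD unadjusted, 0.68 SD Tukey-adjusted and 25 points at 10/25 in both arms, depend only on the planned 25 per arm and on the normality and counts assumed above. With fewer completers they would be wider. They are enough to show that a non-significant test would not demonstrate similarity. The 12% to 68% range for a closed ANOVA gate rests on an assumed 0.5 SD drug difference and on the control positions tabulated; it is not a forecast for this trial.

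**What to change.** Make two changes to the Statistical Analysis Plan.

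1. **Replace the descriptive sentence.** Summarise EAT-10, VHI-10, NDI and VAS by arm and visit with mean, SD, median and quartiles. Summarise Bazaz and complications by arm with counts and percentages.
2. **Add an estimation paragraph.** For each primary outcome, report the ketorolac-dexamethasone difference and each drug-control difference with a 95% confidence interval, whatever the overall p-value. Use Tukey-adjusted intervals for mean differences and, for Bazaz, a risk difference at a cut stated in advance. Label intervals for secondary outcomes as descriptive. State that similar efficacy will not be concluded from p ≥ 0.05.

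The cost is a few sentences and some table programming, with no new data or visits. The downside is more intervals: three primary outcomes × six postoperative visits × three pairs = 54. Tukey's method adjusts only across the three pairs within one outcome and visit, so the plan should acknowledge the remaining multiplicity.

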Study Protocol and Statistical Analysis Plan

The Effect of IV NSAID's and Corticosteroids on Dysphasia and Dysphonia Following ASDF

NCT04650893

Recent Date of Approval: 1/19/2023

Study Protocol

Background & Rationale

Dysphagia and dysphonia are the most common postoperative complications following anterior cervical discectomy and fusion (ACDF). While most postoperative dysphagia and dysphonia is transient, severe cases place the patient at risk for malnutrition, aspiration, pneumonia, airway obstruction, persistent cough, and death. The reported prevalence of dysphagia varies from 3% to 67% and dysphonia from 1% to 51%. The variability is a result of the different ways in which dysphagia and dysphonia are measured and defined. There are many different classification systems for dysphagia, the Eating Assessment Tool-10 (EAT-10) has proven to be reliable, valid, treatment-responsive, and multiculturally versatile. Scores of 3 or greater qualify as clinically relevant dysphagia and scores of 15 or greater qualify as severe dysphagia, which is associated with a higher risk of aspiration. The Voice Handicap Index-10 (VHI-10) has proven to be reliable, valid, and expedient tool to evaluate for dysphonia. Scores greater than 11 are indicative of clinically significant dysphonia. Recent research suggests that these are appropriate patient reported outcome measures (PROMs) to evaluate for dysphagia and dysphonia after cervical spine surgery. Local and intravenous (IV) steroids have been shown to reduce dysphagia and prevertebral soft-tissue swelling following ACDF. A recent study compared the efficacy of local versus intravenous steroids on the likelihood of developing dysphagia and dysphonia after ACDF. It found that both yielded better PROMs for dysphagia compared the control group, with a reduced number of patients reporting severe dysphagia with local steroid application within the first 2 weeks post-op. Local corticosteroids have been associated with impaired wound healing, esophageal complications, and pseudoarthrosis, particularly when administered in the retropharyngeal space. In the study mentioned above, 2 patients in the local corticosteroid group (out of 29 total) developed pseudoarthrosis. Perioperative ketorolac has been shown to have no adverse effect on spinal fusion when administered for < 2 days, or for >2 days at a dose of < 120 mg/day. Current standard of care processes include both IV or local steroid use as well as no steroid use in decreasing the risks of dysphagia or dysphonia post operatively. There are no current specific or routinely used methods in using steroid or no steroidal treatments to those receiving this surgical procedure.

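### Fisher's exact test ignores the order of the Bazaz grades, a primary outcome; with four well-spread grades and moderate to large effects this costs about 11–20 points of power at 25 per arm

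*Combined protocol and SAP*

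**What the plan says.** The Statistical Analysis Plan section of the combined document states: "For dysphagia, primary outcome measures will be the Bazaz classification and the EAT-10". The Objectives section agrees, and Methods lists "Bazaz classification for dysphagia" among the questionnaires collected before surgery and at six postoperative visits.

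The tests are assigned by type of variable. For categorical data, "Fisher's exact test will be used to evaluate associations between treatment groups and categorical measures at each time point". ANOVA or Kruskal-Wallis, "depending on the distribution of the data, will be utilized to compare continuous variables between the groups". No trend test, rank test or ordinal regression is named for Bazaz. Of the longitudinal models the section says only "Mixed effect models also will be explored", and it gives them no ordinal form.

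The Design section fixes the size: "Once 25 from each of the 3 groups have completed the study, the study will cease enrollment". No power calculation, target effect or expected grade distribution appears anywhere.

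**The concern.** A classification is categorical, so under this division Bazaz goes to Fisher's exact test. That test treats the grades as unordered labels. The trial, however, asks whether ketorolac or dexamethasone makes dysphagia milder, which is a directional question. A test that ignores order spreads its power over every pattern in which three arms can differ. With three arms and four grades that is (3 − 1) × (4 − 1) = 6 degrees of freedom, against 2 for a rank comparison of three arms.

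At 25 completers per arm there is little power to spare. What is at stake is a lower chance of detecting a real shift on a primary outcome, mainly at the visits where dysphagia is common. Those are probably the early ones, since the Background describes most cases as transient. The point is limited to Bazaz: EAT-10 is a score and can already be tested under the ANOVA or Kruskal-Wallis sentence.

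**Working it through.** The plan gives no power figure, so there is nothing to reproduce. The check compares the power of the two tests under stated assumptions.

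**Inputs from the document.** Three arms, 1:1:1, 25 completers per arm (Design, Methods). Two-sided 0.05 (Statistical Analysis Plan). Dysphagia prevalence 3% to 67% (Background & Rationale).

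**Assumed.** Four ordered grades from none to severe, the control distributions below, and the odds ratios. None of these is in the document.

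**Step 1: what each test uses.** With the margins fixed, Fisher's test (Fisher-Freeman-Halton form) ranks tables by their probability, ∏(row totals)! × ∏(column totals)! / (N! × ∏ cell counts!). Exchanging two grade columns leaves this unchanged, so order plays no part. Kruskal-Wallis compares mean mid-ranks, which do depend on order.

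**Step 2: the shift.** For an arm with odds ratio OR against control, at each cut k: odds(grade ≤ k, treated) = OR × odds(grade ≤ k, control). Example: controls 33/32/22/13% have cumulative proportions 0.33, 0.65 and 0.87. With OR = 4 the odds 0.493, 1.857 and 6.692 become 1.970, 7.429 and 26.77, giving cumulative proportions 0.663, 0.881 and 0.964. The treated grades are then about 66/22/8/4%.

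**Step 3: power.** 2,000 simulated trials per setting (simulation standard error at most √(0.25/2000) = 1.1 points per power); Fisher p-values from 999 permutations; tie-corrected Kruskal-Wallis. Each cell shows Fisher / Kruskal-Wallis power in %, with the loss in points in brackets. Odds ratios are (ketorolac, dexamethasone) against control.

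| Control grades, % (dysphagic) | OR (2,4) | OR (1,4) | OR (3,3) |
|---|---|---|---|
| 33/32/22/13 (67%) | 44.3 / 61.6 (17.3) | 53.1 / 72.8 (19.7) | 36.9 / 55.7 (18.8) |
| 50/25/15/10 (50%) | 38.1 / 53.1 (15.0) | 46.7 / 63.9 (17.2) | 35.9 / 49.3 (13.4) |
| 65/18/11/6 (35%) | 29.2 / 40.0 (10.8) | 32.5 / 47.1 (14.6) | 26.5 / 38.3 (11.8) |
| 80/11/6/3 (20%) | 16.4 / 22.0 (5.6) | 18.9 / 24.4 (5.5) | 18.2 / 23.4 (5.2) |
| 90/6/3/1 (10%) | 7.5 / 11.1 (3.6) | 6.9 / 8.5 (1.6) | 7.8 / 13.6 (5.8) |

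With no effect, Fisher rejected in 3.8–4.9% of trials and Kruskal-Wallis in 3.7–5.1%, so the gain is not bought with false positives.

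**Step 4: other effect sizes.**
- Both arms at OR 4: losses 17.6, 18.8 and 15.0 points at 67, 50 and 35% dysphagic. Both at OR 6: 10.6, 14.0 and 15.6.
- Both at OR 2: about 8 points at 67% and 50%, 5 at 35%, and 1–2 at 20% and 10%.
- OR 10 at 67%: 94.8 / 98.7, a loss of 3.9, because both tests are near their ceiling.

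**Step 5: sensitivity to the other assumptions.**
- *Other spread distributions.* Across 36 three-arm settings (25/25/25/25, 20/30/30/20, 40/30/20/10 and 15/30/35/20; OR 3, 4 and 6; both arms shifted, one shifted, or graded), the loss was 9.6–22.4 points, typically about 16. In 32 of the 36 it rounded to 11–20.
- *Concentrated grades.* 60/25/10/5 with OR 3–6: 9–14 points. 80/14/5/1: about 2–9.
- *Number of grades.* Three grades: about 8–14 points. Five grades: about 19–25. Yes/no only: −0.3 to 3.5.
- *Fewer patients.* 20 per arm, even grades, OR 3: 31 / 46, a loss of about 16.
- *Non-monotone differences.* Here the ranking reverses. Two arms at 33/32/22/13 against one at 58/7/7/28: 76.4 / 11.0. One arm at 33/32/22/13 against two at 55/8/8/29: 72.1 / 7.2.

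**The case against.** The strongest case against has five parts.

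- **The assignment is inferred.** The plan never attaches Fisher's test to Bazaz by name, does not list the grades, and does not say whether they would be collapsed to present or absent. This stands as a limit, and collapsing would cut the loss to almost nothing. But sending a classification to the categorical test is the natural reading, and if something else was meant, one sentence settles it.
- **The 11–20 points depend on favourable conditions.** They need grades that are spread out, effects above OR 2 but short of the ceiling, and four grades. The largest losses use the top of the prevalence range, and at later visits the loss is probably a few points. Calling 65/18/11/6 well spread is generous. All of this stands, and the figure must be quoted with its conditions.
- **Fisher's test is valid.** It controls type I error and is far stronger for non-monotone differences. That is true, but such differences are not the benefit the trial seeks.
- **EAT-10 is also primary for dysphagia.** The dysphagia question therefore does not rest on Bazaz alone. This lowers the importance, but Bazaz is still listed as a primary outcome in its own right.
- **No analysis was completed, and Kruskal-Wallis would not cure the small sample.** In the three main patterns it reaches only 38–73% power at 35–67% dysphagic. Both statements are correct. They bear on the consequence, not on whether the plan names a suitable test.

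**Conclusion.** The concern holds. Read plainly, the plan compares an ordered primary outcome with a test that ignores order, and nothing else in the document repairs this. For a consistent shift the loss runs from about 1 to 20 points of power under four assumed grades. It is about 11–20 points where 35–67% of controls are dysphagic and effects are moderate to large, and small where dysphagia is rare, the effect is weak, or power is near its ceiling. Three grades would make it somewhat smaller and five somewhat larger.

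The direction needs only more than two ordered grades and a shift in one direction. The size rests on assumed grades, distributions and odds ratios. This is an avoidable loss of efficiency and not a failure of validity. Because no analysis was completed, it affects no reported result; it matters if the plan is reused or the collected data are analysed.

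**What to change.** State in the Statistical Analysis Plan:

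- Bazaz is compared across arms with Kruskal-Wallis and between pairs with Wilcoxon rank-sum tests, adjusted for the three comparisons (for example Holm). At present a pairwise adjustment is given only after ANOVA.
- The effect is reported as a proportional-odds odds ratio with 95% CI. Where grades are too sparse for that model, report the Mann-Whitney probability of a milder grade with 95% CI.
- EAT-10 is analysed as a score, with an order-based test if it is ever cut into more than two classes.
- Fisher's exact test is kept for the binary complications.

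The cost is wording only, with no extra data. There are two downsides. Power is lost if the arms differ in a non-monotone way, and the effect estimate needs the proportional-odds assumption. That odds ratio is also non-finite when an arm has no dysphagia at all. For an arm with OR 4 and a control rate p, the chance is q^25, with q = 4(1 − p) / [4(1 − p) + p]:

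- p = 35%: q = 2.6/2.95 = 0.881, chance about 4%
- p = 20%: q = 3.2/3.4 = 0.941, chance about 22%
- p = 10%: q = 3.6/3.7 = 0.973, chance about 50%

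The Mann-Whitney fallback is therefore needed, most of all at the later visits.

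### The five questionnaires are completed before surgery, but the SAP gives the pre-operative score no role in the group comparisons and does not define its role in the exploratory mixed model, so some precision goes unused at 25 completers per arm

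*Combined protocol and SAP*

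**What the plan says.** The Methods section states that patient questionnaires "will be collected preoperatively and at 1 day" and at five later visits up to 1 year. It lists EAT-10, VHI-10, NDI, VAS and Bazaz, so every questionnaire outcome has a pre-operative value and six post-operative ones.

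The Statistical Analysis Plan makes EAT-10, VHI-10 and Bazaz primary, and NDI and VAS secondary. For continuous outcomes: "Analysis of variance (ANOVA) or the Kruskal-Wallis test, depending on the distribution of the data, will be utilized to compare continuous variables between the groups". After a significant overall ANOVA, "pairwise comparisons will be performed and adjusted using" Tukey's method. For categorical outcomes, Fisher's exact test "will be used to evaluate associations between treatment groups and categorical measures at each time point". None of these sentences names a baseline covariate, a change score or stratification by pre-operative status.

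Mixed models are exploratory only, with "time, treatment group, and time x treatment group interaction terms as fixed effects" and a random intercept. The SAP does not say whether the pre-operative visit is a level of time, a covariate or left out.

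The Design section ends enrolment as follows: "Once 25 from each of the 3 groups have completed the study". The SAP closes with: "No analysis was ultimately completed due to poor follow-up and lack of data".

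**The concern.** A pre-operative score that predicts the later score explains part of the between-patient variation. A comparison that ignores it leaves that variation in the error term. With 25 completers per arm there is little precision to spare. There may be fewer at a given visit, since the Methods section notes that "many times patients are feeling better and do not return for all suggested follow-up".

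Validity is not at stake: under randomisation the unadjusted tests keep their type I error. What could be lost is power, and narrower intervals for the three pairwise contrasts.

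The mixed model adds an ambiguity. Depending on how the pre-operative visit enters, the time-by-treatment term is either a difference between arms in change from baseline or a difference in post-operative level. These have different variances, and as written the choice could be made after the data are seen.

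**Working it through.** **Inputs from the documents.** Three arms, 1:1:1, 25 completers per arm, two-sided 0.05, Tukey adjustment for pairs. No effect size, SD, power, dropout rate or pre/post correlation is given.

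**The plan's own figure.** The 25 per arm cannot be reproduced, because nothing is given to derive it from. It can be characterised. The pairwise difference detectable with 80% power, without multiplicity adjustment, is (1.960 + 0.842) × √(2/25) = 0.79 SD. At the Tukey critical value it is (2.393 + 0.842) × √(2/25) = 0.92 SD.

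**Assumptions.** A pairwise difference of 0.8 SD, normal data, and rho from 0 to 0.6.

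**Formulas, n = 25 per arm.**
- Tukey critical t = q(0.95; 3, df)/√2 = 2.393 (ANOVA, df 72) and 2.394 (ANCOVA, df 71).
- Average cost of estimating the covariate slope: f = 1 + 1/(72 − 2) = 1.0143.
- Contrast variance relative to unadjusted: (1 − rho²) × f. For example, at rho 0.5: 0.75 × 1.0143 = 0.761.
- Break-even: rho = √(1 − 1/f) = 0.119.
- Power: noncentral t with noncentrality 0.8 × √(25/2)/√ratio.
- Half-width of the Tukey simultaneous 95% interval: t × √(2/25 × ratio). Unadjusted: 2.393 × 0.283 = 0.677 SD. (An ordinary, unadjusted-for-multiplicity 95% half-width would be about 0.56 SD.)

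| Analysis | Variance ratio | Power | Tukey half-width (SD) |
|---|---|---|---|
| Unadjusted | 1 | 66.8% | 0.677 |
| ANCOVA, rho 0 | 1.014 | 66.1% | 0.682 |
| ANCOVA, rho 0.2 | 0.974 | 68.1% | 0.668 |
| ANCOVA, rho 0.3 | 0.923 | 70.8% | 0.651 |
| ANCOVA, rho 0.5 | 0.761 | 80.0% | 0.591 |
| ANCOVA, rho 0.6 | 0.649 | 86.5% | 0.546 |

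**The plan's actual sequence.** Simulating the overall F test followed by Tukey (40,000 trials per rho, third arm equal to the lower arm) gives 66–67% unadjusted. With ANCOVA it gives 65.6%, 67.7%, 70.9%, 79.9% and 86.2% at the same five rho values.

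**Fewer patients at a visit.**

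| Per arm | f | Break-even rho | Unadjusted | ANCOVA at rho 0, 0.2, 0.3, 0.5, 0.6 |
|---|---|---|---|---|
| 20 | 1.0182 | 0.13 | 55.2% | 54.3%, 56.3%, 58.9%, 68.7%, 76.4% |
| 15 | 1.0250 | 0.16 | 41.4% | 40.4%, 42.0%, 44.3%, 53.2%, 61.0% |

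**Scores piled up at zero.** This is closer to what might be expected of EAT-10 and VHI-10. The simulation (20,000 trials) used latent normal scores, a 0.8 SD shift in one arm, integer scores cut at 0 and 40, and 30% at zero post-operatively in the other two arms; all are assumptions. It compared the overall Kruskal-Wallis test, with power of about 79%, with Quade's rank ANCOVA.

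| At zero before surgery | Rank ANCOVA power at latent rho 0, 0.2, 0.3, 0.5, 0.6 |
|---|---|
| 80% | 79.1%, 79.5%, 80.3%, 84.0%, 85.8% |
| 50% | 79.2%, 79.9%, 82.0%, 86.9%, 90.1% |

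Type I error of rank ANCOVA in these settings was 0.049 to 0.055.

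**Mixed model.** If the pre-operative visit is an ordinary level of time, the change contrast at one visit has variance 2(1 − rho) relative to the unadjusted post-operative contrast: 1.4 at rho 0.3, 1.0 at 0.5 and 0.6 at 0.7. Below rho 0.5 this reading is less precise than ignoring the baseline, so its role matters.

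**The case against.** The strongest objection is that this is an efficiency option, not an error. One-way tests are legitimate in a small randomised trial, and the benefit depends on a correlation that the documents do not give. The range examined runs from a 1.4% rise in variance to a 35% fall, which is compatible with no useful gain. The larger gains may fall mainly on secondary outcomes. With 80% of pre-operative scores at zero, the gain is about 1 point at latent rho 0.2–0.3 and 4 to 7 points at 0.5–0.6. With 90% at zero (also an assumption; 6,000 trials), it is about 0.6–0.7 points and 3–4.5 points respectively. All of this stands, and it limits the size of the point.

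Two objections concern the reading of the SAP. Its wording on continuous variables is loose enough to cover change scores, so strictly the plan states no use of the baseline rather than ruling one out. For the mixed model, treating the pre-operative assessment as one more level of time is a natural reading. Both are fair, but neither fills the gap: no change score is specified, and that reading of the model is the one that loses precision at low correlation.

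Finally, adjustment cannot make up for missing patients. Falling from 25 to 15 per arm takes unadjusted power from 67% to 41%, and ANCOVA at rho 0.3 recovers 3 points. That is true. It bears on the trial's main difficulty, not on whether a baseline already scheduled for collection should be used.

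**Conclusion.** The point holds. The plan collects a pre-operative value for every questionnaire, gives it no stated use in the ANOVA, Kruskal-Wallis or Fisher comparisons, and leaves its role in the exploratory model undefined.

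The trade-off favours adjustment. At 25 per arm the cost, if the baseline is uninformative, is under 1 point of power; the gain is about 4 points at rho 0.3 and 13 at rho 0.5. These figures rest on the assumed 0.8 SD difference, normality and rho. The expectation of a small gain for the primary EAT-10 and VHI-10, and a larger one for NDI and VAS, is also an assumption. The change is worthwhile but not essential. As no analysis was completed, it matters only if the data are analysed later or the plan is reused.

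**What to change.** - **Continuous scores:** at each post-operative visit, replace one-way ANOVA with ANCOVA containing arm and the pre-operative value of the same score. Keep the Tukey-adjusted pairwise comparisons and report them with 95% confidence intervals, stating that these are simultaneous.
- **Where Kruskal-Wallis would have been used:** use rank ANCOVA, or a proportional-odds model with the pre-operative score.
- **Exploratory mixed model:** state the role of the pre-operative visit. Either model the post-operative visits only, with the pre-operative score and its interaction with visit as covariates, or keep that visit as a level of time with its mean constrained equal across arms.
- **Bazaz:** an ordinal model with the pre-operative grade beside Fisher's exact test is optional. It adds little if nearly all pre-operative grades are the same.

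**Cost.** No new data, visits or forms. One degree of freedom per single-visit model, and about six in the mixed model if the score-by-visit interaction spans the six post-operative visits. If the baseline proves uncorrelated with the outcome, contrast variance rises by 1.4% at 25 per arm and 2.5% at 15. Otherwise, a few SAP sentences and a little extra analysis work.
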